8.1.2 Handling missing data

For the purposes of assigning duration for AEs, partial or missing AE dates will be handled as follows:

- If the day of the month is missing, the onset day will be set to the first day of the
 month unless it is the same month and year as the first dose of trial IMP. In this
 case, the onset date will be assumed to be the date of the first dose of trial IMP.
- If the onset day and month are both missing, the day and month will be assumed to be January 1, unless the event occurred in the same year as the first dose of trial IMP. In this case, the event onset will be assumed to be the day and month of the first dose of IMP.
- A completely missing onset date will be assumed to be the date of the first dose of trial IMP.

End dates:

- If the day of the month is missing, the end day will be set to the last day of the month.
- If the end day and month are both missing, the day and month will be assumed to be December 31.
- A completely missing end date will be assumed to be the minimum of date of study discontinuation and date of data extract.
- If the imputed end date is less than the onset date, use the onset date as the imputed end date.

For the purpose of assigning prior or concomitant flag for medications/vaccinations, partial or missing medication/vaccination dates will be handled as follows:

End dates:

- If end day is missing and month/year are non-missing, then day is assumed to be the last day of the month.
- If end day/month are missing and year is non-missing, then day and month are assumed to be the end of the year (31DECYYYY).

Page 15 of 36 Version: 3.0 Date: 08 MAY 2024

 If imputed end date is less than the start date, use the start date as the imputed end date.

Start dates:

- If the start date year is missing, the start date is set to one day prior to IMP start date
- If the start date year is less than the year of the IMP first dose date, then:
 - If the month is missing, the start date is assumed to be mid-year point (01JULYYYY).
 - Else if the month is not missing, the start date is assumed to be mid-month point (15MONYYYY).
- If the start date year value is greater than the year of the IMP first dose date, then:
 - If the day and month is missing, the start date is assumed to be the year start point (01JANYYYY).
 - Else if the month is not missing, the start date is assumed to be the month start point (01MONYYYY).
- If the start date year value is equal to the year of the IMP first dose date:
 - If the month is missing or the month is equal to the month of the IMP first dose date, then the start date is assumed to be same day as the IMP first dose date.
 - Else if the month is less than the month of the IMP first dose date, the start date is assumed to the mid-month point (15MONYYYY).
 - Else if the month is greater than the month of the IMP first dose date, the start date is assumed to be the month start point (01MONYYYY).

If complete end date is available and the start date assumed from the steps above is greater than the end date, then the assumed start date should be set to the end date.

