8 STATISTICAL ANALYSES

8.1 General considerations

In general, all summaries will be displayed by individual vaccine DL and combined placebo. A total group, combining all subjects on placebo and active vaccine, will be presented in addition for accounting (subject disposition), demographics and other baseline characteristics and protocol deviations as applicable unless otherwise specified.

No formal statistical comparisons between vaccine DL of BNT165b1 and placebo will be performed. Missing data, other than that described for partial or missing dates for AEs/concomitant medications/vaccinations (as described below) will not be imputed.

Continuous variables will be summarized using the following descriptive statistics: number of subjects with non-missing data (n), mean, SD, median, minimum (min) and maximum (max).

Categorical variables will be summarized by absolute and relative frequencies (n and %) of subjects in each category and the number of subjects with missing data ('missing' category will be presented if there is one or more missing value).

For event-driven occurrence data (e.g., adverse event, concomitant medication, etc.) percentages will be based on the number of subjects in the analysis set (N). For reported visit data (e.g., lab etc.) percentages will be based on the number of subjects with non-missing values (n).

The rates of binary endpoints such as safety variables (systemic and local reactions) will be provided.

Page 13 of 36 Version: 3.0 Date: 08 MAY 2024

All data collected during the trial will be listed based on safety set unless otherwise specified. The trial day will be presented as appropriate. Listings will be sorted by dose level, site number, subject number, and date of assessment or date of onset (if applicable).

All trial data will be presented at the visit as assigned in the Case Report Form (CRF). No windowing of data for the purposes of assigning to a visit will occur. Unscheduled assessments will not be included in summaries/analysis but will be included in the listings.

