8.1.1 General definitions

Baseline is defined as last available value prior to first dose of trial IMP.

Generally, if there are multiple pre-baseline assessments available for a particular day, the assessment that is closest to the day (and time if collected) of the first dose of a trial treatment will be used as the baseline value.

Change from baseline: Unless otherwise specified, this will be calculated as follows:

Change from baseline = post-baseline assessment value – baseline assessment value.

If either the baseline or post-baseline assessment value is missing, the change from baseline is set to missing as well.

Body mass index (BMI) will be calculated as follows:

BMI
$$\left(\frac{\text{kg}}{\text{m}^2}\right) = \frac{\text{Weight (kg)}}{\text{Height(m)}^2}$$

Temperatures collected in °F will be converted to °C as follows:

$$^{\circ}C = (^{\circ}F - 32) * 5/9$$

Duration will be calculated as follows:

• Duration = last observation date - first observation date + 1.

For conversion of days to months or years the following rules will be applied:

- 1 month = 30.4375 days
- 1 year = 365.25 days

Trial Day will be calculated as follows:

- If assessment/onset date < date of first IMP dose, then trial day = assessment date
 date of first IMP dose
- If assessment/onset date >= date of first IMP dose, then trial day = assessment/onset date - date of first IMP dose + 1

That is, trial day 1 indicates the date of first IMP dose.

The day relative to dose 2 or dose 3 will be calculated as follows:

Statistical Analysis Plan (SAP)

BNT165-01

Page 14 of 36

Version: 3.0

Date: 08 MAY 2024

 If assessment/onset >= date of second IMP dose and < date of third IMP dose, then day relative to dose 2 = assessment/onset date - date of second IMP dose + 1

If assessment/onset >= date of third IMP dose, then
 day relative to dose 3 = assessment/onset date – date of third IMP dose + 1

All trial data will be presented at the visit in the visit assigned in the Case Report Form (CRF)/visit assigned in external data. No windowing of data for the purposes of assigning to a visit will occur.

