- Any missed assessment will be considered as "no reaction". (e.g., if a subject has grade 1 headache on day 1 and 2, missing data on day 3 and 4 and grade 2 headache between day 5 and 7, this should be considered as 2 separate headache events, one of 2 days duration and one of 3 days duration. The maximum duration (3 days in this example) and the maximum severity (grade 2 in this example) would be used for the analysis.).
- For events that persist beyond Day 7, the duration of the reactogenicity event will be derived using the start and the end date of the AE (as recorded on the AE page).
- Onset day, defined as the first day of reporting any severity, will be derived for each recorded local reaction.

A reactogenicity overview summary will include the subjects with

- Any local reaction within 7 days of IMP injection
- Any local reaction that persisted beyond 7 days of IMP injection

Page 20 of 36 Version: 3.0 Date: 08 MAY 2024

Analyses in the overview summary will be provided for reactions of any grade and for reactions of grade ≥3. Analyses will be provided within 7 days of each IMP injections and overall regardless of the number of injections.

The number and percentage of subjects reporting local reactions (pain at the injection site, erythema/redness, induration/swelling) within 7 days after IMP dose will be summarized by maximum severity and cumulatively regardless of the severity. This summary will include categories "Any", "Grade 1", "Grade 2", "Grade 3" and "Grade 4".

All local reaction summaries will be based on the safety set but excluding subjects without any e-diary data throughout the 7 days after vaccination.

In addition, local reactions will also be summarized by:

- Maximum duration (days) of each local reaction after each IMP injection and overall regardless of the number of injections
- Onset day of each local reaction after each IMP injection and overall regardless of the number of injections

For analyses overall across all injections, the subject will only be counted once for each local reaction reported.

Bar charts with the number of subjects for each local reaction throughout 7 days after each dose will be plotted. The bars will be divided into severity categories to highlight the proportions of subjects by maximum severity. In addition, listing of subjects in the safety set with reported local reactions, will be provided.

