8.5.3 Systemic reactions

The systemic reactions assessed and recorded in the e-diary are vomiting, diarrhea, headache, fatigue/tiredness, Myalgia-muscle pain, Arthralgia-joint pain, chills and fever from Day 1 through Day 7 inclusive, where Day 1 is the day of each IMP injection. The derivations for systemic reactions will be handled similar to the way local reactions are handled for presence of event, severity level, duration, and onset day.

Fever is defined as an oral temperature $\geq 38.0^{\circ}\text{C}$ (100.4°F). Temperatures collected in degrees Fahrenheit will be converted to degrees Celsius using (°F – 32) × 5/9.

Statistical Analysis Plan (SAP) BNT165-01

Page 21 of 36 Version: 3.0 Date: 08 MAY 2024

The highest oral temperature for each day will be recorded in the e-diary and the temperature from Day 1 through Day 7 will be graded as described in Table 5.

Solicited systemic reactions will be categorized as mild, moderate, severe or potentially life-threatening) and graded from 1 to 4 as described in Table 5. The categories and grades are based on the FDA Guidance for Industry: "Toxicity Grading Scale for Healthy Adult and Adolescent Volunteers Enrolled in Preventive Vaccine Clinical Trials"⁴. Any systemic reaction of Grade 3 or higher will be confirmed by the investigator along with an assessment if it meets the definition of Grade 4.

Page 22 of 36 Version: 3.0 Date: 08 MAY 2024

Table 5: Systemic reaction grading scale

	Mild (Grade 1)	Moderate (Grade 2)	Severe (Grade 3) ^a	Potentially life- threatening (Grade 4) ^a			
Vomiting	1 to 2 times in 24 h	>2 times in 24 h	Requires intravenous hydration	Emergency room visit or hospitalization for hypotensive shock			
Diarrhea	2 to 3 loose stools in 24 h	4 to 5 loose stools in 24 h	6 or more loose stools in 24 h	Emergency room visit or hospitalization for severe diarrhea			
Headache	Does not interfere with activity	Some interference with activity	Prevents daily routine activity	Emergency room visit or hospitalization for severe headache			
Fatigue / tiredness	Does not interfere with activity	Some interference with activity	Prevents daily routine activity	Emergency room visit or hospitalization for severe fatigue			
Myalgia - muscle pain	Does not interfere with activity	Some interference with activity	Prevents daily routine activity	Emergency room visit or hospitalization for severe muscle pain			

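### A solicited reaction with no recorded end date enters the duration summary as an observed value running to study discontinuation or data extract, which distorts the mean, SD and maximum of that table

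*SAP*

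**What the plan says.** SAP 8.1 says missing data are not imputed, but it exempts missing or partial dates for AEs, medications and vaccinations. SAP 8.1.2 gives the AE rule under the lead-in "For the purposes of assigning duration for AEs, partial or missing AE dates will be handled as follows". An end date lacking only its day, or its day and month, moves to the end of that month or year. For an end date with nothing recorded: "A completely missing end date will be assumed to be the minimum of date of study discontinuation and date of data extract".

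SAP 8.5.2.1 uses e-diary entries for reactions that resolve within the seven-day window. Once a reaction goes past Day 7, its duration is "derived using the start and the end date of the AE (as recorded on the AE page"). SAP 8.5.3 carries this over to systemic reactions: "The derivations for systemic reactions will be handled similar to the way local reactions are handled for presence of event, severity level, duration, and onset".

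The planned output is "Maximum duration (days) of each local reaction after each IMP injection and overall regardless of the number of injections". The general formula in SAP 8.1.1 is "Duration = last observation date - first observation date + 1". The default statistics for continuous variables in SAP 8.1 are "number of subjects with non-missing data (n), mean, SD, median, minimum (min) and maximum (max").

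The SAP has no rule that caps, censors or flags an unresolved reaction in this summary, or counts such reactions alongside it.

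**The concern.** A reaction still ongoing at the end of observation has a censored duration: the truth is at least that long. A reaction that resolved without a recorded date has an unknown duration, and running it to the end overstates it. The SAP treats both as observed values.

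The substitute date adds a further problem. SAP 8.2 reports completers and discontinuations separately. A completer has no discontinuation date, so on a literal reading the minimum reduces to the extract date. That date is not an observation on the subject. It can be later than the last contact, and it differs between data cuts. SAP Section 5 plans an interim analysis that includes reactogenicity, and cohorts open one after another. The same unresolved reaction could therefore receive different durations by cut and by cohort.

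Missing end dates are foreseen. Protocol 8.3.3 allows for AEs with no final status at the last visit, and Protocol 10.4.3 provides outcome categories for unresolved, resolving and unknown.

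At stake is whether the mean, SD and maximum duration by dose level describe reactogenicity or the state of the date fields.

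**Working it through.** **1. Length of follow-up.** The schedule of activities gives a span of 546 days. The planned phases after the first dose are about 26 and 52 weeks: (26 + 52) × 7 = 546, which agrees. By visit day, Dose 3 is on Day 183 and Visit 14 is 365 days later: 183 + 365 = Day 548. The steps below use Day 548.

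**2. Imputed duration.** Apply the SAP 8.1.1 formula with the end date at Day 548 and onset on the dosing day (Days 1, 57 and 183). The ranges use the visit windows: ±2 d for Dose 2, ±7 d for Dose 3 and ±10 d for Visit 14.

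| Reaction after | Calculation | Days | Range |
|---|---|---|---|
| Dose 1 | 548 − 1 + 1 | 548 | 531–565 |
| Dose 2 | 548 − 57 + 1 | 492 | 473–511 |
| Dose 3 | 548 − 183 + 1 | 366 | 356–376 |

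If a completer's end date is set to an extract E days after Visit 14, each figure grows by E. The documents give no extract date.

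**3. Dependence on the cut.** The planned interim follows the visit 28 days after Dose 2: 57 + 28 = Day 85. If the extract fell on that day for a given subject, the same Dose 1 reaction would be recorded as 85 − 1 + 1 = 85 days, against 548 or more at the end.

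**4. Effect on the summary.** Assume n subjects contribute, n − 1 of them with duration t and one with imputed duration L. Then mean = t + (L − t)/n and SD = (L − t)/√n. The documents give no distribution of durations, so t is an assumption.

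- n = 16 (a full vaccine group), t = 2, L = 548: mean = 2 + 546/16 = 36.1; SD = 546/4 = 136.5; median 2; maximum 548.
- n = 16, t = 2, L = 492: mean 32.6; SD 122.5; median 2.
- n = 16, t = 2, L = 366: mean 24.8; SD 91.0; median 2.
- n = 16, t = 5, L = 548: mean 38.9; SD 135.8; median 5.
- n = 12 (pooled placebo, 3 × 4), t = 2, L = 548: mean 47.5; SD 157.6; median 2.
- n = 8, t = 2, L = 548: mean = 2 + 546/8 = 70.25; SD = 546/√8 = 193.0; median 2.

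Only subjects who report a given reaction contribute to its duration, so the working n may be below 16.

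**5. Comparison.** With n = 16 and t = 2, leaving the unresolved case out of the observed statistics and counting it separately gives a mean of 2.0 days.

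**The case against.** The strongest reply is that the trigger should be rare and its effect visible. The rule applies only when even the year of the end date is missing. Protocol 10.4.3 requires start and end dates in the CRF, Protocol 8.3.3 requires follow-up to resolution or stabilisation, and discrepant data are queried. The planned statistics already include the median, which barely moves. Reactions persisting past seven days are counted separately in the reactogenicity and AE overviews, and listings would show the outlier. All of this stands and keeps the point minor. It does not correct the mean, SD and maximum in the duration table itself.

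A second reply is textual. The parenthesis in SAP 8.5.2.1 about dates recorded on the AE page might mean that no imputation is intended. That reading is possible, but SAP 8.1.2 is written for AE durations, and the AE tables in SAP 8.5.4 are counts and percentages. The reaction-duration summary is the planned output that needs an AE duration. Without imputation, an undated reaction would have no computable duration and would drop out, so the SAP would still need a rule.

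A third reply is that the discontinuation date may be meant to include the completion date. The SAP does not say so. Even then, the value would still be treated as observed.

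A reader might also infer that taking the start from the AE page loses the seven diary days, because a reaction becomes reportable as an AE only after Day 7. The documents do not support that. Protocol 10.4.3 asks for the date of onset, and SAP 8.5.2.1 measures from the start of the event. Entering Day 8 would be a site error, not a feature of the plan.

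**Conclusion.** The point holds as a minor flaw in one descriptive summary. One reaction with a completely missing end date can dominate the mean, SD and maximum duration for its group: 36.1 and 136.5 days, against a typical 2, in a group of 16 after Dose 1. This rests on three assumptions: that SAP 8.1.2 feeds the reaction-duration summary, which is the natural reading; that the end date is set at the scheduled final visit; and that other reactions last about 2 days. With a typical 5 days, the mean is 38.9.

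Two stronger inferences fail. Durations above 500 days are not general at the scheduled final visit: they apply to Dose 1 reactions and the overall summary, while Dose 2 gets there only at the edge of the visit windows and Dose 3 gives about 366. Nor are the primary results compromised. The primary estimands are frequencies and proportions, severity grading does not use end dates, no hypothesis is tested, and no formal comparison with placebo is planned.

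**What to change.** Add to SAP 8.1.2 and 8.5.2.1, with effect for 8.5.3, that in the reaction-duration summary:

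- a completely missing end date is not treated as observed, but is censored at the subject's last contact and never at the data-extract date;
- such values are flagged in the table and listing;
- the number of reactions ongoing or with unknown end date is reported per dose level, for each injection and overall;
- duration is presented as median and range with censored values marked, and any mean or SD is restricted to observed durations. Censoring at Visit 14 alone would still put 548 days into the mean.

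This needs no new data. The cost is a few SAP sentences, a censoring flag in the derivation and one more row in the table.

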8.2 Subject disposition

The number of subjects who were screened and randomized and the number and percentage of subjects who were vaccinated (safety set), vaccinated with one, two and all the three doses will be summarized. In addition, the number and percentage of subjects who discontinued treatment along with a summary of the primary reason for treatment discontinuation as reported in the electronic case report form (eCRF) will be summarized.

Page 16 of 36 Version: 3.0 Date: 08 MAY 2024

The number and percentage of subjects who completed the trial and who discontinued the trial will be summarized.

The number and percentage of subjects that discontinued the trial before dose 2, after dose 2 but before dose 3 and after dose 3 together with the primary reason for discontinuation will be summarized.

The number and percentage of subjects in each analysis set will be summarized using the randomized set. In addition, for each analysis set, the number and percentage of subjects excluded from the analysis set will be presented, along with a summary of the reasons for exclusion.

Subject disposition and inclusion in analysis sets will be listed based on the screened set.

The number and percentage of subjects in the safety set with key PDs will also be presented.

8.3 Baseline characteristics

8.3.1 Demographics and baseline characteristics

The following demographic and baseline characteristics data will be summarized using the safety set:

- Age (years)
- Sex (male or female)
- Childbearing potential (yes or no)
- Race (Black or African American, American Indian or Alaska Native, Asian, Native Hawaiian or Other Pacific Islander, White, Not reported, Unknown, Other). Multiple race respondents will be summarized in a separate category (Multiple).
- Ethnicity (Hispanic or Latino, Not Hispanic or Latino, Not reported and Unknown)
- Height (cm)
- Weight (kg)
- Body Mass Index (BMI (kg/m²)) continuous and in categories (<18.5 kg/m², 18.5 to < 25.0 kg/m², 25.0 to < 30 kg/m², \ge 30 kg/m²)

Viral screen data (HIV 1 status, HIV 2 status, Hepatitis B status and Hepatitis C status (Positive or Negative)) and the COVID-19 tests data will be listed only.

8.3.2 Prior and concomitant medication /vaccination/procedures/non- drug therapy

Prior and concomitant medications will be defined using medication start and stop dates recorded, relative to the first dose of IMP.

Page 17 of 36 Version: 3.0 Date: 08 MAY 2024

If the medication started and stopped before the date of the first dose of trial IMP, the medication will be assigned as being prior to trial IMP. Otherwise, the medication/procedure will be assigned as being concomitant with trial IMP.

Medications will be coded using the World Health Organization Drug Dictionary (WHO Drug) drug codes of version B3 Sep 2022 or later. Resulting in Anatomical-Therapeutic-Chemical (ATC) codes indicating therapeutic classification.

The number and percentage of subjects who had prior medications/vaccinations and concomitant medications/vaccinations will be summarized by ATC classification level 4 and preferred name by vaccine dose levels of BNT165b1, combined placebo group and total for subjects in the safety set. The ATC codes and preferred names will be presented in alphabetical order.

Concomitant medications administered due to local and systemic reactions during time interval Day 1 to 7 days post each dose will be summarized. Bar chart with the number and percentage of subjects with any CM for local and systemic reactions will be presented.

Concomitant Procedures and Non-drug therapies will be coded using the Medical Dictionary for Regulatory Activities (MedDRA®) coding system version 25.1 or later. Concomitant Procedures and non-drug therapies will be listed only.

